9.4.4. Exploratory Endpoints

The exploratory endpoints are as follows

- Detection of anti-AdV, BKV, CMV, EBV, HHV-6 and/or JCV-specific T cells through Week 26
- Hospitalization readmission rate related to AdV, BKV, CMV, EBV, HHV-6 and/or JCV viremia/disease through Week 26
- Total days in the ICU
- Proportion of patients requiring mechanical ventilation related to AdV, BKV, CMV, EBV, HHV-6 and/or JCV infection or disease through Week 26
- Duration of anti-viral therapy (foscarnet, ganciclovir, cidofovir or other) due to viremia and/or disease through Week 26

The exploratory efficacy analysis will be performed on patients in Cohort OL,

For Cohort OL, results will be presented by stratum and overall, as all patients in Cohort OL receive only ALVR105. Combined summary for patients in Cohort OL will also be provided.

Continuous variable will be summarized by descriptive statistics. Categorical variables will be summarized by frequency count and the percentages by visit and overall.

9.4.5. Safety Analysis

All safety data will be summarized by cohort, stratum, [REDACTED] [REDACTED]. For Cohort OL, results will be presented by stratum and overall, as all patients in Cohort OL receive only ALVR105.. Categorical endpoints will be summarized using the number and percentage of patients within each category. Continuous endpoints will be summarized descriptively with summary statistics (number of non-missing observations, arithmetic mean, standard deviation, median, minimum, and maximum).

Adverse events will be coded using the Medical Dictionary for Regulatory Activities. A treatment emergent adverse event (TEAE) is defined as an AE with onset or worsening on or after the first dose of study treatment. TEAEs will be summarized by System Organ Class and Preferred Term and further by severity (according to the National Cancer Institute [NCI] Common Terminology Criteria for Adverse Events [CTCAE] v5.0) and by relationship to study treatment. The incidence of SAEs will be summarized.

The incidence of AEs of special interest (AESIs), including acute and chronic GVHD and CRS, and their corresponding exact binomial 95% confidence intervals will be presented.

Descriptive statistics will be provided for continuous clinical laboratory, vital sign, and ECG data for both the raw data and change from baseline. Abnormal laboratory results will be graded according to NCI CTCAE v5.0, if applicable. Shift tables, presenting the 2-way frequency tabulation for baseline and the worst post-baseline value according to the NCI CTCAE grade, will be provided for selected clinical laboratory tests.

9.4.6. Other Analyses

The baseline demographics of participants, such as age and gender, etc., will be summarized by cohort and treatment group using frequency counts and percentages for categorical variables and descriptive statistics for continuous variables. Continuous variables will be analyzed using a two-sided, two-sample t-test to test for a difference in means between treatment groups. Categorical variables will be analyzed using a two-sided, Fisher's Exact Test to test for a difference in proportions between treatment groups.

9.5. Interim Analyses

A review by the DSMB will be done when approximately 30 patients in the OL Cohort have completed 30 days of treatment. At this time an assessment of benefit, risk, and process will be done, and study optimization will be considered. [REDACTED]

A sample size re-estimation (SSRE) and futility analyses will be performed.

The planned interim analyses will be described in greater detail in a separate document.

9.5.1. Stopping Criteria

9.5.1.1. Stopping Criteria for Individual Patients

As GVHD and CRS are theoretical safety concerns associated with administration of third-party allogeneic T cells, the incidence and severity of GVHD and CRS will be monitored during the study.

No patients will be permitted to receive subsequent infusions of ALVR105 or placebo if:

1. They develop irreversible, life-threatening, Grade 3 to 4 acute GVHD within 6 weeks, or a Grade 3 to 4 non-hematologic AE within 4 weeks from last ALVR105 dose that is considered related to study treatment administration. If this occurs, the patient's toxicities will be followed until resolution or until the patient's participation in the study ends,
2. Receive any other hematopoietic stem cell product,
3. Receive therapy for relapse of the patient's primary malignancy,
4. Develop Grade 3 or 4 CRS that persists beyond 72 hours.

9.5.1.2. Stopping Criteria for the Study

Treatment assignment will be halted if 3 patients experience SAEs that meet the following criteria:

- CTCAE Grade 3
- Considered related by the Investigator
- Occur during the Treatment Period following the initial dose
- Cannot be reasonably attributed to the patient's underlying disease, other medical condition, or concomitant medications

If this occurs, treatment assignment will not resume until there has been a thorough review of all safety data to date and concluded that it is safe for the study to continue.

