10.1.5.2. Data Safety Monitoring Board

A review by the DSMB will be done when approximately 30 patients have completed 30 days of treatment and throughout the study as indicated in the DSMB charter (see DSMB charter).

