10.1.9.2. Study/Site Termination

The Sponsor or designee reserves the right to close the study site or terminate the study at any time for any reason at the sole discretion of the Sponsor. Study sites will be closed upon study completion. A study site is considered closed when all required documents and study supplies have been collected and a study-site closure visit has been performed.

The Investigator may initiate study-site closure at any time, provided there is reasonable cause and sufficient notice is given in advance of the intended termination.

Reasons for the early closure of a study site by the Sponsor or Investigator may include but are not limited to:

For study termination:

- Discontinuation of further study intervention development

For site termination:

- Failure of the Investigator to comply with the protocol, the requirements of the IRB/IEC or local health authorities, the Sponsor's procedures, or GCP guidelines
- Inadequate or no recruitment (evaluated after a reasonable amount of time) of participants by the Investigator
- Total number of participants included earlier than expected

If the study is prematurely terminated or suspended, the Sponsor shall promptly inform the Investigators, the IECs/IRBs, the regulatory authorities, and any contract research organization(s) used in the study of the reason for termination or suspension, as specified by the applicable regulatory requirements. The Investigator shall promptly inform the participant and should assure appropriate participant therapy and/or follow-up

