1 INTRODUCTION

The purpose of this Statistical Analysis Plan (SAP) is to provide a description of the statistical methods to be implemented for the analysis of data from the Phase 2 open label (OL) cohort of Protocol P-105-202. All the patients in the Phase 2 OL were enrolled, treated, and followed under Protocol Amendment 2 dated 7 April 2021. Data were collected under Protocol Amendment 2 Schedule of Activities ([Appendix 2](#)). The analysis will be based on Protocol Amendment 4 dated 19 October 2021. In addition, the clinically significant infections or episodes of end-organ disease were determined by the clinical investigators in Phase 2. [REDACTED]

The SAP will be finalized prior to Phase 2 database lock. Any deviations from the SAP after database lock will be documented in the final Clinical Study Report (CSR) for the Phase 2 OL cohort. [REDACTED].

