3.6 Data Safety Monitoring Board

An independent Data Safety Monitoring Board (DSMB) will be convened for this study to routinely monitor patient safety and evaluate pre-specified interim analyses to stop the study early. The DSMB will receive summary reports of all SAEs including unexpected SAEs. A DSMB charter, detailing all aspects of the DSMB's composition, scope of review, and procedures will be provided in a separate document. An unblinded statistician will be assigned to the DSMB. This statistician will not be involved in any aspects of study conduct outside of the DSMB, and their role will be defined in the DSMB charter.

A review by the DSMB will be done when approximately 25 to 35 patients in the OL cohort have completed 30 days of treatment. At this time, an assessment of benefit, risk, and endorsement to proceed to Phase 3 will be undertaken.

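### The three-patient halting rule counts related SAEs of CTCAE Grade 3 only, so related life-threatening and fatal SAEs do not count toward it as written

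*Protocol*

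**What the plan says.** Protocol section 9.5.1.2 sets the study-level rule: "Treatment assignment will be halted if 3 patients experience SAEs that meet the following criteria". Four criteria follow:

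- CTCAE Grade 3, given as a single grade;
- "Considered related by the Investigator";
- "Occur during the Treatment Period following the initial dose";
- no other reasonable explanation in the underlying disease, another medical condition or concomitant medication.

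Once the rule is met, assignment stays closed until all safety data to date have been reviewed and the study is judged safe to continue.

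Section 9.5.1.1, immediately before it, sets the rules for ending infusions in an individual patient. There the grades are written as ranges: Grade 3 to 4 for acute GVHD and for related non-hematologic AEs, and for cytokine release syndrome "Develop Grade 3 or 4 CRS that persists beyond 72 hours".

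Oversight outside the rule is described in three places. The DSMB reviews the study at about 30 patients and "throughout the study as indicated in the DSMB charter" (Protocol 10.1.5.2). SAP section 3.6 adds: "The DSMB will receive summary reports of all SAEs including unexpected SAEs". The sponsor may "terminate the study at any time for any reason at the sole discretion of the Sponsor" (Protocol 10.1.9.2).

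**The concern.** A numeric halting rule makes assignment pause first and leaves the judgement for afterwards. As worded, that automatic protection covers only the least severe of the three grades it would be expected to cover. Related SAEs that are life-threatening or fatal have to be caught by discretion. Sites, the CRO and the DSMB would each have to infer that the rule means more than it says, and nothing ensures that they infer the same thing. At stake is continued assignment of new patients to a third-party T cell product after a run of related life-threatening events or deaths, with no pre-specified trigger having been reached.

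**Working it through.** The plan states no operating characteristics for this rule, so there is no figure to reproduce. The check is first textual, then an illustration.

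**Step 1: how the criteria combine.** An SAE counts if it meets the listed criteria, which is naturally read as all four. The causality, timing and attribution criteria narrow the set further. None of them widens the grade.

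**Step 2: what Grade 3 means here.** Section 10.3.3 defines Grade 3 as severe but not immediately life-threatening, Grade 4 as life-threatening and Grade 5 as death. The categories are exclusive for a given event, so a related fatal SAE cannot satisfy a Grade 3 criterion.

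**Step 3: how the protocol writes grades elsewhere.** Sections 7.1 and 9.5.1.1 spell out ranges (3 to 4; 3 or 4). The exclusion criteria and the infusion footnotes in the schedules use a greater-than sign (Grade >2). The single grade in 9.5.1.2 is the exception.

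**Step 4: does another provision add Grade 4 or 5 events to a study-level halt?**

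| Provision | What it does | Automatic study-level halt? |
|---|---|---|
| Protocol 7.1 and 9.5.1.1 | Ends infusions in the affected patient | No |
| Protocol 8.5.1 and 8.5.4.1 | SAEs to the sponsor within 24 hours; fatal or life-threatening SUSARs to regulators within 7 days | No, notification only |
| Protocol 10.1.5.2 and SAP 3.6 | DSMB review and SAE summaries | No numeric trigger given; charter not available |
| Protocol 10.1.9.2 | Sponsor may terminate | No, discretionary |

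**Step 5: illustration of size.** All rates are assumed. Let p3 be the proportion of patients with at least one qualifying Grade 3 SAE, and p45 the further proportion whose only qualifying SAEs are Grade 4 or 5. A patient with both kinds belongs to p3 and counts under either wording. The number of counted patients among n is taken as binomial, with p = p3 as written and p = p3 + p45 if higher grades count:

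P(X ≥ 3) = 1 − (1−p)^n − n·p·(1−p)^(n−1) − [n(n−1)/2]·p²·(1−p)^(n−2)

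Example with n = 30:
- p = 0.05: 1 − 0.2146 − 0.3389 − 0.2586 = 0.188 (after rounding).
- p = 0.05 + 0.05 = 0.10: 1 − 0.0424 − 0.1413 − 0.2277 = 0.589 (after rounding).

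Results for n = 30, near the middle of the planned 25 to 35 open-label patients:

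| Assumed p3 | Assumed p45 | As written | Grade 3 or higher |
|---|---|---|---|
| 1% | 1% | 0.3% | 2.2% |
| 2% | 1% | 2.2% | 6.0% |
| 5% | 2% | 18.8% | 35.1% |
| 5% | 5% | 18.8% | 58.9% |
| 0% | 1% | 0% | 0.3% |
| 0% | 2% | 0% | 2.2% |
| 0% | 5% | 0% | 18.8% |

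Across n = 25 to 35, the 2% plus 1% case runs from 1.3% to 3.3% as written and from 3.8% to 8.7% with the wider criterion. The 5% plus 5% case runs from 12.7% to 25.4% and from 46.3% to 69.4%.

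**The case against.** The literal reading is hard to dispute. The other side argues about practical weight.

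- **Intent.** The sponsor very probably meant Grade 3 or higher, and no safety team would ignore three related deaths because they exceeded Grade 3. That is likely true, but it is a reason to write the intended rule. It does not make the text correct.
- **A lost symbol.** The text was read from PDF, and some characters have dropped out (hyphens in the GVHD staging table, for example). A missing greater-than-or-equal sign cannot be ruled out. Such signs survive in many other places, including the eligibility criteria, so loss here is unlikely. The sponsor can settle it from the source file.
- **Other safeguards.** Rapid SAE reporting, the individual stopping rules, DSMB review and the sponsor's right to terminate all lower the practical risk, and the DSMB charter may hold numeric limits that are not visible here. This stands as mitigation, but nothing visible replaces an automatic halt.
- **Who is affected.** SAP section 1 says: "All the patients in the Phase 2 OL were enrolled, treated, and followed under Protocol Amendment 2". It bases the analysis on Amendment 4 and describes a Phase 2/3 study, so later patients may be assigned under a version with different wording. This also stands. The correction matters only for assignment still governed by this text.
- **Assumed rates.** The probabilities are not evidence about this product, and their sample size is that of a cohort already enrolled. They show how the two wordings differ and nothing more.

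**Conclusion.** The concern holds: section 9.5.1.2, followed as written, leaves related Grade 4 and Grade 5 SAEs out of the three-patient count. The conclusion rests on the wording and on the protocol's own grade definitions, and it does not depend on any assumed rate. The size cannot be estimated from the documents. Under the assumed rates, the gap between the two wordings at n = 30 runs from a fraction of a percentage point when events are rare to about 40 points (58.9% − 18.8% = 40.1) at 5% plus 5%. The finding is limited to this one rule. It does not say that the study could not be stopped after severe events, only that no numeric trigger in these two documents would require a halt. It assumes that the extracted text matches the source and that this version governs some remaining assignment.

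**What to change.** In Protocol section 9.5.1.2, change the first criterion to CTCAE Grade 3 or higher. Use the same wording in the DSMB charter, and confirm it in whichever amendment now governs treatment assignment. The cost is one phrase in the protocol and a matching line in the charter, with no added patients, visits or procedures. The trade-off is that assignment may be paused for review sooner or more often, which is the purpose of the rule.

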^g Clinical laboratory assessments collected as part of standard of care may be used to fulfill these requirements. CBC must include differential and LFTs

must include alkaline phosphatase, bilirubin (direct and indirect); GGT, AST, and ALT. Urinalysis must be performed. Laboratory safety evaluations (hematology, chemistry, and urinalysis) specified in [Section 8.4.4](#) will be performed prior to study drug initiation. These samples will be sent to the appropriate central laboratory(ies) following the procedure(s) described in the study manual(s).

^h For female patients, a urine pregnancy test will be performed at the site prior to study therapy initiation. If the urine pregnancy test result is negative, the patient will be eligible for treatment assignment and the remainder of the Day 1 testing/procedures will be performed. If the urine pregnancy result is positive, the patient must not be assigned to treatment and should reflex to a β -HCG blood test before screen failing. A urine pregnancy test will be performed prior to each treatment for female patients who are of childbearing potential.

ⁱ Viral loads of AdV, BKV, CMV, JCV, and HHV-6 in plasma and of EBV in PCMBs will be measured. Additional post-infusion samples may be collected, as clinically indicated. If patient develops any clinically significant infection of AdV, BKV, CMV, EBV, HHV-6, or JCV at any point during the study periods, infection assessments should be followed prior to initiating standard of care therapy (see [Section 8.3](#)).

^j Patients in Cohort OL will be assigned to ALVR105. Patients in Cohorts A and B will be randomized to either ALVR105 or placebo based upon the last viral load assessed and within 7 days of randomization. Treatment assignment will be about 2 to 3 days before Day 1.

^k Patient peripheral blood mononuclear cells will be assessed for the presence of virus-reactive T cells using enzyme-linked immunospot.

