4. STUDY DESIGN

4.1. Overall Design

This is a Phase 2, multi-center, randomized, double-blind, placebo-controlled, multiple dosing, trial to investigate ALVR105 administered intravenously, with the first dose between 15 and 42 (+7) days after allogeneic HCT, followed by every 2-week infusions until Week 14, in comparison to matching placebo for the prevention of active replication and clearance of active viremia of AdV, BKV, CMV, EBV, HHV-6, and/or JCV in high-risk patients.

This study is comprised of an optional pre-screening period, a screening period, a treatment period, and a follow-up period. The optional pre-screening period is included to allow for the assessment of viral loads for patients who may potentially be eligible for participation in the study prior to actual screening. The screening period may begin at the time of HCT and may vary in length of up to 6 weeks. The treatment period is 14 weeks, and the follow-up period is approximately 12 weeks. Overall, the total duration patient participation in the study is approximately 28 to 32 weeks (up to 6 weeks for screening, 14 weeks of treatment, and 12 weeks of follow-up). The overall enrollment period is anticipated to be approximately 12 months.

Patients will also receive a telephone call follow-up approximately 52 weeks after their last study visit to assess mortality.

There are 3 cohorts (Cohort Open Label [OL],

The first 25 to 35 patients (Cohort OL) will receive ALVR105 for 30 days of open-label dosing to assess and optimize processes. A review by the Data Safety Monitoring Board (DSMB) will be done when approximately 30 patients have completed 30 days of treatment. At this time an assessment of benefit, risk, and process will be done, and study optimization will be considered.

Open label patients will continue in the open label arm.

Patients will be tested at the first assessment during Screening by the central laboratory for AdV, BKV, CMV, EBV, HHV-6, and JCV viremia using polymerase chain reaction (PCR) assays for each virus. Patients will then be tested weekly during Screening until treatment assignment. In **Cohort OL**, patients may test positive or negative for AdV, BKV, CMV, EBV, HHV-6, and/or JCV viremia.

ohort OL will also include a 50% cap for letermovir prophylaxis; Sponsor can revisit this limit based on on-going assessment of feasibility. With respect to other

prophylaxis treatments see the inclusion criteria ([Section 5.1](#)).

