Study therapy (with ALVR105 or placebo) will begin between 15 and 42 (+7) days (inclusive) post- HCT. Administration may begin as early as day 15 post-HCT as long as, in the Investigator's judgment, the patient has met the engraftment criteria. Study therapy will be given at 2-week intervals through Week 14, and the study evaluation will continue through Week 26 (~6 months), with the primary objective of preventing clinically significant infections and/or disease of AdV, BKV, CMV, EBV, HHV-6, and/or JCV through Week 14 and with a secondary objective of preventing clinically significant infections and/or diseases of AdV, BKV, CMV, EBV, HHV-6, and/or JCV through Week 26 (~6 months). 

On the day of treatment assignment (randomization), eligibility for enrollment into the study should be confirmed (including confirmation that HCT has taken place). 

Once enrolled in the study, patients will have study visits scheduled at weekly intervals through Week 14. Following completion of the primary study period at Week 14, all patients will remain in the study through Week 26 in order to continue collecting information on (1) incidence and time to onset of AdV, BKV, CMV, EBV, HHV-6, and/or JCV viremia and/or disease; (2) all adverse events through the treatment period in all patients, including those who have discontinued study treatment but are continuing in the study. For patients who have discontinued, only drug-related SAEs and SAEs leading to death will be collected until Week 26.; and (3) quality of life (QoL) measures using validated patient reported outcome tools. During the follow-up period, study visits will occur monthly after Week 14 until Week 26. Patients will also receive a follow-up call one year after the Week 26 visit to assess mortality.

For patients who develop any clinically significant infection of AdV, BKV, CMV, EBV, HHV-6, and/or JCV, during the primary study period (up to Week 14) or during the follow-up period (after Week 14 and through Week 26) when the Investigator intends to initiate either treatment for viral infection or disease, infection assessments should be conducted ([Section 8.3](#)). These patients will continue to receive infusions of study drug during the treatment period. 

[figure not shown]
Specific procedures to be performed during the trial, as well as their prescribed times and associated visit windows, are outlined in the SoA ([Section 1.3](#)). Details of each procedure are provided in [Section 8](#).

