8.1.3. Treatment period

The treatment period is 14 weeks. Study therapy (with ALVR105 or placebo) will begin between 15 and 42 (+7) days (inclusive) post-HCT. Study therapy will be given at 2-week intervals through Week 14, and the study evaluation will continue through Week 26 (~6 months). The first 25 to 35 patients (Cohort OL) will be assigned to ALVR105 for 30 days of open-label dosing [REDACTED].

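### The study-level toxicity rule in Protocol 9.5.1.2 counts events through each patient's 14-week Treatment Period but acts only on treatment assignment, so it has no consequence after the last assignment in the study

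*Protocol*

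**What the plan says.** Protocol 9.5.1.2 is the only numeric study-level toxicity trigger in the supplied text: "Treatment assignment will be halted if 3 patients experience SAEs that meet the following criteria". The events must be Grade 3, judged related by the investigator and not reasonably explained by other causes. On timing they must "Occur during the Treatment Period following the initial dose". Protocol 8.1.3 fixes that window: "The treatment period is 14 weeks".

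Once the rule fires, "treatment assignment will not resume until there has been a thorough review of all safety data to date" and a conclusion has been reached that the study can safely go on. The section states no other action and does not say who conducts the review.

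Assignment is a single allocation step. Protocol 4.1 equates it with randomization: "On the day of treatment assignment (randomization), eligibility for enrollment into the study should be confirmed". Footnote j to the treatment-period schedules in 1.3 dates it: "Treatment assignment will be about 2 to 3 days before Day 1". Dosing is described separately: "Study therapy will be given at 2-week intervals through Week 14". The individual stopping rules in 9.5.1.1 are likewise worded in terms of further infusions, not assignment.

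On accrual, Protocol 4.1 states: "The overall enrollment period is anticipated to be approximately 12 months".

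**The concern.** The window and the action do not match. The rule keeps counting events for as long as anyone is in the Treatment Period, but it acts only on people not yet assigned.

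This has two consequences. While assignment is open, the rule does not require anyone to decide whether patients already assigned should go on receiving infusions. Once the last patient in the study is assigned, there is nothing left to halt or resume, so a third qualifying event triggers nothing in 9.5.1.2.

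Three related Grade 3 SAEs are the level at which the protocol itself wants safety looked at again. The patients most directly exposed to such a signal are those already being dosed, who may be as young as 1 year. Protocol 4.2 gives a reason for repeated dosing, namely coverage in the absence of virus, so stopping is not obviously right. That is a reason to put the question to the DSMB rather than leave it unaddressed.

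**Working it through.** The plan gives no operating characteristic for the three-patient rule, so there is no stated figure to reproduce. The check is of the length of the gap and of how much dosing falls in it.

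**Inputs**
- Infusion days, from the schedules in Protocol 1.3: Days 1, 14, 28, 42, 56, 70 and 84, which is 7 infusions. Offsets from Day 1 are 0, 13, 27, 41, 55, 69 and 83. They sum to 288, so the mean is 288/7 = 41.14 days.
- End of the Treatment Period: Day 98, offset 97 days.
- Lag from assignment to Day 1: 2 to 3 days (Protocol 1.3, footnote j).
- Enrollment period T: about 12 months (Protocol 4.1), taken as 12 × 30.44 = 365.3 days.
- Assumptions not in the documents: even accrual over T, no dropout, and alternative enrollment periods of 9, 18 and 24 months.

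**Step 1: length of the gap**
- Last infusion after the last assignment: 83 + 2 = 85 to 83 + 3 = 86 days.
- End of the counting window after the last assignment: 97 + 2 = 99 to 97 + 3 = 100 days.

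**Step 2: share of infusions in the gap**

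Under even accrual, an infusion at offset d falls after the last assignment with probability (d + lag)/T. Averaging over the seven infusions gives (41.14 + lag)/T.
- Lag 2: 43.14/365.3 = 11.8%.
- Lag 3: 44.14/365.3 = 12.1%.

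**Step 3: share of Treatment Period patient-time in the gap**

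The same argument over offsets 0 to 97, whose mean is 48.5, gives (48.5 + lag)/T.
- Lag 2: 50.5/365.3 = 13.8%.
- Lag 3: 51.5/365.3 = 14.1%.

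**Step 4: sensitivity to the enrollment period**

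| Enrollment | Infusions after last assignment (lag 2 / lag 3) | Patient-time after last assignment (lag 2 / lag 3) |
|---|---|---|
| 9 months | 15.7% / 16.1% | 18.4% / 18.8% |
| 12 months | 11.8% / 12.1% | 13.8% / 14.1% |
| 18 months | 7.9% / 8.1% | 9.2% / 9.4% |
| 24 months | 5.9% / 6.0% | 6.9% / 7.0% |

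Neither formula contains the sample size.

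**Step 5: cross-check by direct count**

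Placing 25, 30 or 35 patients at even steps over 52 weeks, with infusions exactly every 2 weeks and no lag, gives 12.0%, 12.9% and 12.2% of infusions and 15.0%, 14.7% and 14.5% of patient-time. This agrees with steps 2 and 3 to about one percentage point. It checks the arithmetic only; a cohort of that size is not the whole study.

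**The case against.** The strongest reply is that 9.5.1.2 already requires a review of all safety data and a conclusion that it is safe for the study, not merely assignment, to continue. Those data include patients on treatment. A reader might infer that the rule leads to no review of continued dosing at all. The documents do not support that while assignment is open, because the required review can cover dosing. What remains is that the rule does not require a decision on assigned patients, and that the review is tied to resuming assignment and so is not called for once assignment is complete.

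A reader might also place the gap at the end of the open-label cohort. That does not follow either. Cohorts A and B come after it, and a late event in an open-label patient could still halt their assignment.

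A third tempting inference is that assigned patients would be dosed without oversight. Several provisions say otherwise:
- SAEs reach the sponsor within 24 hours (Protocol 8.5.1), and immediate safety concerns go to the sponsor for a decision on that patient (Protocol 8).
- Under Protocol 7.1 and 9.5.1.1, a related Grade 3 to 4 non-hematologic event within 4 weeks of a dose ends that patient's infusions. Most affected patients would therefore already have stopped, and the open question concerns the others.
- The DSMB reviews safety throughout the study under its charter (Protocol 10.1.5.2), receives SAE summaries (SAP 3.6) and reviews events of special interest (SAP 3.5.2).
- The sponsor may terminate at any time (Protocol 10.1.9.2).

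These safeguards stand and lower the severity. None is written as a consequence of the third qualifying event. The charter, which was not supplied, may contain such a link. The SAP Introduction also refers to Protocol Amendment 4, and the stopping rule in that amendment cannot be confirmed from the supplied text.

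**Conclusion.** The concern holds in a limited form. The counting window of 9.5.1.2 outlasts its only action by about 99 to 100 days after the last assignment in the whole study, and a third qualifying event in that time has no consequence under the rule. Before then, the rule requires a review but no decision on patients already assigned, and it names no body to conduct it.

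At the protocol's 12 months, about 12% of scheduled infusions and 14% of Treatment Period patient-time lie in the gap. Across enrollment of 24 down to 9 months the ranges are about 6% to 16% and 7% to 19%. The figures rest on even accrual and no dropout. The planned DSMB review after about 30 open-label patients makes perfectly even accrual uncertain. They describe how much dosing and follow-up is involved, not the chance that the rule fires or the harm that would result.

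This is a worthwhile correction rather than a critical flaw, held with medium confidence because the charter is unseen. The SAP reports that the open-label patients have already been enrolled, treated and followed, so the practical benefit is for any cohort still governed by this wording.

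**What to change.** Add two statements to Protocol 9.5.1.2:
1. The third qualifying event promptly convenes the existing DSMB, whether or not assignment is open, through the end of the last patient's Treatment Period.
2. While any patient still has infusions due, the review must include a recommendation on whether patients already assigned continue them.

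No automatic dose hold is proposed; any interim hold stays with the DSMB and sponsor. Align the charter text with these statements. If the charter already provides this, a citation to it in 9.5.1.2 is enough.

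The cost is two sentences and a possible ad hoc DSMB meeting. The change does not by itself delay any infusion.
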